7.1 Primary Efficacy Analysis

Progression free survival (PFS) is defined as the time of randomization to date of death from any cause, date of relapse/progression, or the last follow-up date, whichever comes first. The Kaplan-Meier method will be used to estimate PFS for each cohort. The method of Brookmeyer and Crowley will be used to construct 95% confidence interval.

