Study Design	
Randomized parallel 2-cohort phase 2 study of Elotuzumab given at 10 mg/kg weekly during induction in combination with lenalidomide (either 25 mg or 10 mg) in patients with multiple myeloma who progress or relapse serologically while on single agent lenalidomide maintenance. Patients will be randomized to either (1) cohort A = lenalidomide 25 mg PO daily days 1-21 with Elotuzumab or (2) cohort B = lenalidomide 10 mg PO daily days 1-21 with Elotuzumab. We selected the dose of Elotuzumab at 10 mg/kg weekly dosing followed by monthly infusion of 20 mg/kg based on the safety and tolerability profile in the published phase 3 study and other studies of combination therapy with bortezomib,¹⁻³ as well as an ongoing study in combination with pomalidomide (NCT02612779). Elotuzumab will be administered intravenously on days 1, 8, 15, and 22 during the first 2 cycles, then on day 1 of each cycle starting third cycle. The combination therapy with Elotuzumab and lenalidomide will be continued until further progression of myeloma (based on response criteria) or intolerance.
 
Combination dosing schedule:

--------------	---

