- Elotuzumab 10 mg/kg IV weekly (days 1, 8, 15 and 22) for 2 cycles, then 20 mg/kg every 4 weeks
- Lenalidomide 10 mg PO daily days 1-21 out of a 28-day schedule

Response assessment:

The Consensus on Uniform Reporting of Response will be used to evaluate response.⁴ Myeloma patients enrolled in this clinical study will be assessed for disease response after every cycle. Time to disease progression will be defined as the time from the day first Elotuzumab treatment to the time of myeloma progression.

4 Study population

Patients with multiple myeloma who demonstrate evidence of serologic relapse/progression while on lenalidomide maintenance given as part of **first** line therapy (including upfront high-dose chemotherapy followed by autologous hematopoietic cell transplantation (HCT)) without symptomatic relapse/progression. Lenalidomide maintenance is defined as **single agent** lenalidomide therapy of any doses up to 15 mg PO daily for up to 28 days (28-day cycle). Relapse/progression is defined as increase of 25% from the lowest response value (for either serum or urine M-spikes), absolute increase in serum M-spike ≥ 0.5 g/dL, absolute increase in urine M-spike ≥ 200 mg/24hour, or the difference between involved and uninvolved free light chain (FLC) levels of absolute increase with > 10 mg/dl (only for those without measurable serum and urine M-spikes) There will be 30 subjects in each cohort for total accrual of 60 subjects.

Patients must have baseline evaluations performed prior to the first dose of study drug and must meet all inclusion and exclusion criteria. Results of all baseline evaluations, which assure that all inclusion and exclusion criteria have been satisfied, must be reviewed by the Principal Investigator or Co-investigators prior to enrollment of that patient. In addition, the patient must be thoroughly informed about all aspects of the study, including the study visit schedule and required evaluations and all regulatory requirements for informed consent. The written informed consent must be obtained from the patient prior to enrollment. The following criteria apply to all patients enrolled onto the study unless otherwise specified.

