4.1 Inclusion criteria

1. Patients with multiple myeloma who demonstrate evidence of serologic relapse/progression while on lenalidomide maintenance given as part of **first** line therapy (including upfront high-dose chemotherapy followed by autologous hematopoietic cell transplantation (HCT)) without symptomatic relapse/progression.

Lenalidomide maintenance is defined as **single agent** lenalidomide therapy of any doses up to 15 mg PO daily for 14-28 days (28-day cycle). Relapse/progression is defined as increase of 25% from lowest confirmed response value in one or more of the following criteria: Serum M –protein (absolute increase must be ≥ 0.5 g/dl)

Serum M-protein increase >1 g/dl, if the lowest M component was >5 g/dl

Urine M –protein (absolute increase must be > 200 mg in 24 hours)

In patients without measurable serum and urine M-protein levels, the difference between involved and uninvolved FLC levels (absolute increase must be > 10 mg/dl)

For patients relapsing from complete remission, relapse is defined as:

Reappearance of serum or serum M-protein by immunofixation or electrophoresis.

2. Male or female patients aged ≥ 18 years old

3. Ability to provide written informed consent obtained prior to participation in the study and any related procedures being performed

4. Measurable disease with at least 1 of the following assessed within 28 days prior to Cycle 1 Day 1:

A. Serum M-protein ≥ 0.5 g/dL,

B. Urine M-protein ≥ 200 mg/24 hour,

C. In subjects without measurable serum or urine M-protein, serum free light chain (SFLC) > 10 mg/dL (involved light chain) and an abnormal serum kappa lambda ratio

5. Patients must meet the following laboratory criteria within 28 days prior to Cycle 1, day 1:

- Absolute neutrophil count (ANC) $\geq 1 \times 10^9/L$
- Hemoglobin $\geq 10 \text{ g/dL}$
- Platelet count $\geq 75,000/\text{mm}^3$
- AST and ALT $\leq 2.5 \times \text{ULN}$
- Serum bilirubin $\leq 1.5 \times \text{ULN}$
- Serum Creatinine clearance $\geq 50\text{ml}/\text{min}$

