Partial response	$\geq 50\%$ reduction of serum M-protein plus reduction in 24 h urinary M-protein by $\geq 90\%$ or to <200 mg per 24 h; If the serum and urine M-protein are unmeasurable, a $\geq 50\%$ decrease in the difference between involved and uninvolved FLC levels is required in place of the M-protein criteria; If serum and urine M-protein are unmeasurable, and serum-free light assay is also unmeasurable, $\geq 50\%$ reduction in plasma cells is required in place of M-protein, provided baseline bone marrow plasma-cell percentage was $\geq 30\%$. In addition to these criteria, if present at baseline, a $\geq 50\%$ reduction in the size (SPD) ^{§§} of soft tissue plasmacytomas is also required
Minimal response	$\geq 25\%$ but $\leq 49\%$ reduction of serum M-protein and reduction in 24-h urine M-protein by 50–89%. In addition to the above listed criteria, if present at baseline, a $\geq 50\%$ reduction in the size (SPD) ^{§§} of soft tissue plasmacytomas is also required
Stable disease	Not recommended for use as an indicator of response; stability of disease is best described by providing the time-to-progression estimates. Not meeting criteria for complete response, very good partial response, partial response, minimal response, or progressive disease
Progressive disease ^{¶¶}	Any one or more of the following criteria:

Response criteria*

	Increase of 25% from lowest confirmed response value in one or more of the following criteria: Serum M-protein (absolute increase must be ≥ 0.5 g/dL); Serum M-protein increase ≥ 1 g/dL, if the lowest M component was ≥ 5 g/dL; Urine M-protein (absolute increase must be ≥ 200 mg/24 h); In patients without measurable serum and urine M-protein levels, the difference between involved and uninvolved FLC levels (absolute increase must be >10 mg/dL); In patients without measurable serum and urine M-protein levels and without measurable involved FLC levels, bone marrow plasma-cell percentage irrespective of baseline status (absolute increase must be $\geq 10\%$); Appearance of a new lesion(s), $\geq 50\%$ increase from nadir in SPD ^{SS} of >1 lesion, or $\geq 50\%$ increase in the longest diameter of a previous lesion >1 cm in short axis; $\geq 50\%$ increase in circulating plasma cells (minimum of 200 cells per μ L) if this is the only measure of disease

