Special attention should be given to the emergence of a different monoclonal protein following treatment, especially in the setting of patients having achieved a conventional complete response, often related to oligoclonal reconstitution of the immune system. These bands typically disappear over time and in some studies have been associated with a better outcome. Also, appearance of monoclonal IgG κ in patients receiving monoclonal antibodies should be differentiated from the therapeutic antibody.

§§

Plasmacytoma measurements should be taken from the CT portion of the PET/CT, or MRI scans, or dedicated CT scans where applicable. For patients with only skin involvement, skin lesions should be measured with a ruler. Measurement of tumor size will be determined by the SPD.

¶¶

Positive immunofixation alone in a patient previously classified as achieving a complete response will not be considered progression. For purposes of calculating time to progression and progression-free survival, patients who have achieved a complete response and are MRD-negative should be evaluated using criteria listed for progressive disease. Criteria for relapse from a complete response or relapse from MRD should be used only when calculating disease-free survival.

|||

In the case where a value is felt to be a spurious result per physician discretion (e.g., a possible laboratory error), that value will not be considered when determining the lowest value.

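### Could a patient who is stable or improving on study be scored as a PFS event because section 7.1 names no reference value for progression?

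*Combined protocol and SAP*

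**What the plan says.** Section 7.1 counts PFS from randomisation to "date of death from any cause, date of relapse/progression, or the last follow-up date, whichever comes first". It names no reference value.

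Section 6.2 has the investigator determine response from the study's disease assessments and the IMWG criteria in Appendix B. There, progressive disease begins with "Increase of 25% from lowest confirmed response value in one or more of the following criteria", with an absolute serum rise of at least 0.5 g/dL. No time window is attached to the lowest value.

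Inclusion criterion 1 in section 4.1 uses almost the same sentence for the relapse that qualifies a patient: "Relapse/progression is defined as increase of 25% from lowest confirmed response value in one or more of the following criteria". At entry the lowest value can only be one reached before the study.

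The only rule on which values may serve as the lowest is the Appendix B footnote on spurious results: "that value will not be considered when determining the lowest value". It does not mention pre-study values.

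Other passages bear on the point indirectly. The Synopsis and section 3 say the combination "will be continued until further progression of myeloma (based on response criteria) or intolerance". Section 3 also states: "Time to disease progression will be defined as the time from the day first Elotuzumab treatment to the time of myeloma progression".

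**The concern.** Every patient enters after a serologic relapse, and one phrase serves for both entry and outcome. If the pre-study nadir still counted after randomisation, a patient who entered on a serum rise would meet the serum part of the PFS event on day 1. Such a patient would go on meeting it unless the M-protein fell a long way. Requiring two samples gives no protection, because a stable value is easily confirmed.

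Each cohort of 30 is judged against a fixed 7-month null, and the investigator decides on progression. False early events would shorten PFS and work against the regimen. Uneven scoring between investigators would add noise to the comparison of cohorts A and B. Section 6.2 also bars a response where there is evidence of progression, so ORR might seem exposed too.

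**Working it through.** **1. The plan's own power.** Inputs from section 7: n = 30 per cohort, medians 7 and 12 months, accrual A = 24 months, follow-up F = 12 months, one-sided alpha 0.05. The plan names no test. I assume exponential PFS, uniform accrual and a one-sample test on the log hazard.

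- Hazards: λ0 = ln 2/7 = 0.0990 and λ1 = ln 2/12 = 0.0578 per month; ratio 7/12 = 0.583.
- Event probability: 1 − [exp(−λF) − exp(−λ(A+F))]/(λA).
- Null: 0.884 × 30 = 26.5 events. Alternative: 0.729 × 30 = 21.9 events.
- Power: Φ{[ln(12/7) − 1.645/√26.5] × √21.9} = 84.8%.

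The stated 85% is reproduced. Choosing an on-study reference changes none of these inputs.

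**2. What the literal reading does to one patient** (invented serum values). Pre-study nadir 0.2, entry 1.6, on study 0.75 g/dL.

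- Change from entry: (1.6 − 0.75)/1.6 = 53% fall, in the serum range for partial response.
- Change from nadir: 0.75 − 0.2 = 0.55 g/dL, or 0.55/0.2 = 275% rise, which is progression.

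To escape, the value must fall below 0.2 + 0.5 = 0.7 g/dL, so the required fall is 1 − 0.7/entry:

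| Entry (g/dL) | Fall must exceed |
|---|---|
| 1.0 | 30% |
| 1.2 | 42% |
| 1.6 | 56% |
| 2.0 | 65% |

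**3. Whether that reading can be meant.** The entry thresholds in section 4.1 (serum at least 0.5 g/dL, urine above 200 mg/24 h, light-chain difference above 10 mg/dL) equal or exceed those in Appendix B (0.5, 200 and above 10). So anyone admitted on one of these rises would meet progressive disease at randomisation.

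Now let a share f of a cohort be scored at the first 28 days (28/30.44 = 0.92 months) while true PFS has median 12. The apparent median is 12 × log2[2(1 − f)]: 10.2 months at f = 10%, 8.1 at 20%, 5.8 at 30% and 3.2 at 40%. At 50% it collapses to 0.92 months. A 7-month null median for patients already in serologic relapse would need most of them to show falls of the size in step 2 at once. Section 7 cannot have that event in mind.

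**4. What the other passages imply.**

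| Place | Implication |
|---|---|
| Section 6.2 with Table 6-1; section 6.4 | Scoring rests on study assessments, and these begin at screening |
| Synopsis; section 3 | Progression beyond the relapse that led to entry |
| Section 3 | Time to progression starts at the first elotuzumab dose |
| Appendix B, partial response | Refers to study baseline ("provided baseline bone marrow plasma-cell percentage was") |
| Section 7 | The 7-month figure is for patients already in serologic relapse |

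None of these sets a value, but all point the same way.

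**5. Size if some patients were nevertheless mis-scored.** Simulated cohorts of 30, one-sample log-rank against median 7, true median 12. The two figures use the variance forms E and (O+E)/2.

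| Share scored at day 28 | Cutoff 36 months | Cutoff at 28th event in cohort |
|---|---|---|
| 0% | 82.4% / 85.3% | 86.4% / 88.5% |
| 10% | 60.5% / 64.7% | 69.5% / 72.6% |
| 20% | 35.5% / 39.6% | 47.6% / 51.0% |

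The shares are assumptions. They describe sporadic error, not the literal rule, under which far more patients would be events.

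**6. ORR.** The Appendix B footnotes that carry this bar refer to progressive or new bone lesions, and one adds extramedullary plasmacytomas. They do not mention an M-protein still above an old nadir. An effect on ORR is not shown.

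**The case for a change.** The strongest case is that a primary endpoint should not rest on convention. The investigator scores progression, no central review is described, and the comparison is with a fixed null. Three wrongly scored patients per cohort (10% of 30) would cost about 20 points of power at 36 months. Even a reader who resets at entry must choose between the screening and cycle 1 day 1 values, and Appendix B dates responses at the first test without naming progression. One sentence using values already collected would settle the reference.

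What stands is that the reference is not written down, and that a clarifying sentence would do no harm. What does not stand is the step from silence to a live risk. To mis-score, an investigator would have to record progression for a patient whose M-protein is stable or has halved since entry, in a trial that admits patients because they have relapsed serologically. The choice between two pre-dose values and the dating of progression are ordinary details that analysts settle before database lock.

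Separately, the documents disagree on how often response is assessed (Table 6-1 note 4 against sections 3, 6.2 and 6.4). They also differ on when treatment ends (Synopsis, Duration of Treatment, and sections 3, 5.2 and 5.9). Those passages must be reconciled, but they do not bear on the reference value.

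**Conclusion.** No change to the plan follows. Section 7.1 and Appendix B leave out a detail that analysts would fill sensibly: the rise is measured from the study baseline, or from any lower confirmed on-study value. The contrary reading makes the entry criterion the endpoint and conflicts with the medians on which the trial was sized.

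Under the sensible reading there are no false events from this source, and the sample size, the stated 85% power (84.8% recomputed) and the analysis are unaffected. The losses in step 5 would be serious if they occurred, but they depend on mis-scored shares that no passage supports, and on a one-sample log-rank test that the plan does not name. The conclusion assumes that investigators score from the study's own assessments, as section 6.2 directs.

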7.2 Secondary Endpoints Analyses

- Overall response rate (ORR) with Elotuzumab and lenalidomide for each cohort
- Minimum response (MR) or better rate with Elotuzumab and lenalidomide for each cohort
- Time to next treatment (TTNT) for each cohort
- Comparison of clinical outcomes (cohort A versus B)
- Fc γ RIIia receptor polymorphisms (homozygous for high-affinity V (VV) allele vs. low affinity F (FF) allele)
- Effect of Elotuzumab added to lenalidomide on phenotypic characteristics of the immune infiltrate and correlation with therapeutic efficacy

The Kaplan-Meier method or Gray method ⁴⁰ will be used to estimate the survival rate or incidence rate for the time-to-event endpoints with or without competing risks, respectively. The association of time-to-event endpoints with potential predictors will be explored using Cox proportional regression model or Fine-Gray regression model,⁴¹ as appropriate. The 95% confidence interval for binary endpoint will be computed using the exact binomial distribution (e.g., Clopper-Pearson method) and the association with binary endpoint will be examined by the logistic regression model.

8 REGULATORY CONSIDERATIONS

8.1 Institutional Review Board/Ethics Committee Approval

The protocol for this study has been designed in accordance with the general ethical principles outlined in the Declaration of Helsinki. The review of this protocol by the IRB/EC and the performance of all aspects of the study, including the methods used for obtaining informed consent, must also be in accordance with principles enunciated in the declaration, as well as ICH Guidelines, Title 21 of the Code of Federal Regulations (CFR), Part 50 Protection of Human Subjects and Part 56 Institutional Review Boards.

The Investigator will be responsible for preparing documents for submission to the relevant IRB/EC and obtaining written approval for this study. The approval will be obtained prior to the initiation of the study. The approval for both the protocol and informed consent must specify the date of approval, protocol number and version, or amendment number.

Any amendments to the protocol after receipt of IRB/EC approval must be submitted by the Investigator to the IRB/EC for approval. The Investigator is also responsible for notifying the IRB/EC of any serious deviations from the protocol, or anything else that may involve added risk to subjects.

Any advertisements used to recruit subjects for the study must be reviewed and approved by the IRB/EC prior to use.

8.2 Informed Consent

The Investigator must obtain informed consent of a subject or his/her designee prior to any study related procedures as per GCPs as set forth in the CFR and ICH guidelines.

Documentation that informed consent occurred prior to the subject's entry into the study and the informed consent process should be recorded in the subject's source documents. The original consent form signed and dated by the subject and the person obtaining the consent prior to the subject's entry into the study must be maintained in the Investigator's study files.

8.3 Subject Confidentiality

In compliance with United States federal regulations, the Investigator permit its representatives and, when necessary, representatives of the FDA or other regulatory authorities to review and/or copy any medical records relevant to the study in accordance with local laws.

Should direct access to medical records require a waiver or authorization separate from the subject's statement of informed consent, it is the responsibility of the Investigator to obtain such permission in writing from the appropriate individual.

8.4 Study Record Requirements

The Investigator must ensure that the records and documents pertaining to the conduct of the study and the distribution of the study drug, that is copies of CRFs and source documents (original documents, data, and records [e.g., hospital records; clinical and office charts; laboratory notes; memoranda; subject's diaries or evaluation checklists; SAE reports, pharmacy dispensing records; recorded data from automated instruments; copies or transcriptions certified after verification as being accurate copies; microfiches photographic negatives, microfilm, or magnetic media; x-rays; subject files; and records kept at the pharmacy, at the laboratories, and at medicotechnical departments involved in the clinical study; documents regarding subject treatment and study drug accountability; original signed informed consents, etc.]) be retained by the Investigator for as long as needed to comply with national and international regulations (generally 2 years after discontinuing clinical development or after the last marketing approval). The Investigator agrees to adhere to the document/records retention procedures by signing the protocol.

8.5 Premature Discontinuation of the Study

The responsible local clinical Investigator and the sponsor have the right to discontinue this study at any time for reasonable medical or administrative reasons. Possible reasons for termination of the study could be but are not limited to:

- Unsatisfactory enrollment with respect to quantity or quality.
- Inaccurate or incomplete data collection.
- Falsification of records.
- Failure to adhere to the study protocol.

9 REGULATORY AND REPORTING REQUIREMENTS

9.1 Adverse Events

(All serious adverse events (SAE) must be reported to the Medical Monitor BMS within 24 hours of the investigational staff's knowledge; this includes any event that occurs during the participation of the trial regardless of associated therapy, severity or relationship)

9.2 Serious Adverse Event (SAE) Definition

A serious adverse event is one that at any dose (including overdose):

- Results in death
- Is life-threatening¹
- Requires inpatient hospitalization or prolongation of existing hospitalization
- Results in persistent or significant disability or incapacity²
- Is a congenital anomaly or birth defect
- Is an important medical event³
- Suspected positive pregnancy

- 1 “Life-threatening” means that the subject was at immediate risk of death at the time of the serious adverse event; it does not refer to a serious adverse event that hypothetically might have caused death if it were more severe.
- 2 “Persistent or significant disability or incapacity” means that there is a substantial disruption of a person’s ability to carry out normal life functions.
- 3 Medical and scientific judgment should be exercised in deciding whether expedited reporting is appropriate in situations where none of the outcomes listed above occurred. Important medical events that may not be immediately life-threatening or result in death or hospitalization but may jeopardize the patient or may require intervention to prevent one of the other outcomes listed in the definition above should also usually be considered serious. Examples of such events include allergic bronchospasm requiring intensive treatment in an emergency room or at home, blood dyscrasias or convulsions that do not result in inpatient hospitalization, or the development of drug dependency or drug abuse. A new diagnosis of cancer during the course of a treatment should be considered as medically important.

